8.3 Planned Interim Analyses (if applicable)

Not applicable.

8.4 Final Analysis Plan

To assess change in providers' HPV vaccine recommendation behavior, we will compare providers' mean recommendation quality index scores between baseline and 12-week follow-up using Wilcoxon signed-rank tests. To assess changes in providers' cognitions and perceptions of their social environments, we will use Wilcoxon signed-rank tests to compare mean scores for each survey item and the knowledge index item (scores ranging from 1-5) between the baseline and post-workshop surveys and the baseline and 12-week follow-up surveys.

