2.2 Rationale

Our study seeks to evaluate the feasibility of Checkup Coach, a quality improvement (QI) coaching intervention, including a mobile app, that we have developed to deliver HPV vaccine communication training. At the provider level, Checkup Coach is designed to improve HPV vaccine communication via ongoing assessment and tailored feedback.

At the clinic level, the app will provide quality improvement tools, including graphs of clinics' and providers' HPV vaccine coverage (i.e., % of patients vaccinated), for tracking shared goals for improvement. We will conduct this study to evaluate the feasibility of using the QI coaching intervention to improve HPV vaccine communication in primary care settings. If successful, this study will inform the future development of a randomized controlled trial to examine the impact of the Checkup Coach intervention on HPV vaccine uptake.

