5.3 Strategies for Recruitment and Retention

The KPWA Medical Director for Preventive Care will identify KPWA primary care clinics in the Puget Sound/Spokane area that administer HPV vaccine to adolescent patients, ages 11-12. He will invite clinics to participate in the study by contacting each site's clinical director. Once clinical directors agree to have their clinics participate, study staff will invite all primary care providers who regularly treat 11-12 year old patients in each clinic to participate.

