7.2 Enrollment/Baseline

Enrollment and pre-workshop data collection will occur simultaneously from July – September 2021. Communication workshops and post-workshop data collection will occur in the same period, from July – September 2021.

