8 STATISTICAL CONSIDERATIONS

8.1 Study Hypotheses

The Checkup Coach intervention will increase providers' HPV vaccine recommendation quality score.

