8.2 Sample Size Considerations

We will test our hypothesis that Checkup Coach will increase providers' overall recommendation quality over the 12-week study period with approximately 20 providers. We acknowledge that our trial is underpowered to detect small differences or control for multiple testing. The purpose of a feasibility study is to estimate effect sizes for powering a large-scale RCT. By piloting our intervention in 5 or more different clinics, our study is designed to provide the data needed to lay this groundwork.

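### Does section 8.4 need a clinic-level check because its signed-rank tests treat about 20 providers from 5 or more clinics as independent?

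*Combined protocol and SAP*

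**What the plan says.** Section 8.4 is the whole analysis plan. For the primary outcome it will "compare providers' mean recommendation quality index scores between baseline and 12-week follow-up using Wilcoxon signed-rank tests"; the survey items and knowledge index get the same test. Clinic is not mentioned, and no interval is specified.

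Recruitment runs through clinics. Under section 5.3, once a clinical director agrees, "study staff will invite all primary care providers who regularly treat 11-12 year old patients in each clinic to participate". Sections 4 and 8.2 expect approximately 20 providers. Section 8.2 gives the aim and the role of the clinics: "The purpose of a feasibility study is to estimate effect sizes for powering a large-scale RCT", and "By piloting our intervention in 5 or more different clinics, our study is designed to provide the data needed to lay this groundwork". It admits low power for small differences and for multiplicity control, but does not mention clustering.

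Some parts of the intervention are shared. Section 2.2 describes app tools that include "graphs of clinics' and providers' HPV vaccine coverage (i.e., % of patients vaccinated), for tracking shared goals for improvement". Section 7.2 refers to workshops in the plural ("Communication workshops and post-workshop data collection will occur in the same period"), and section 6.2 has each provider attend one. No section says that sessions are organised by clinic.

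**The concern.** The signed-rank test assumes that the paired differences are independent of one another. Taking each provider's change removes stable differences between clinics, such as a clinic whose scores are high at both time points. It does not remove variation between clinics in the change itself. If colleagues pursue a common goal and improve together, 20 providers carry less information than 20 independent ones. The p-value is then too small, and any provider-level interval placed around the effect is too narrow.

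This seems to matter because section 8.2 presents the study as a source of effect sizes for a later trial and names the spread over clinics as part of what makes it useful, while the analysis uses no clinic information. A reader might therefore expect a count of providers per clinic and a supportive clinic-level estimate.

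**Working it through.** **Inputs from the documents.** About 20 providers (sections 4 and 8.2); 5 or more clinics (section 8.2), hence an average of at most 20/5 = 4 per clinic; a signed-rank test on the change from baseline to 12 weeks (section 8.4). The sample size has no stated derivation, so there is no figure of the plan's to reproduce.

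**Assumptions, none from the documents.** ICC of the change score from 0 to 0.20, the clinic layouts below, a two-sided 5% test, normally distributed changes, and complete 12-week data from all 20 providers.

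**Step 1: loss of information.** Design effect DE = 1 + (mA − 1) × ICC, where mA = Σm²/Σm and m is the number of providers in a clinic. Effective n = 20/DE, and interval width is multiplied by √DE. At ICC 0.10:

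| Layout | mA | DE | Effective n | √DE |
|---|---|---|---|---|
| 5 clinics of 4 | 80/20 = 4.0 | 1.30 | 15.4 | 1.140 |
| 8, 5, 4, 2, 1 | 110/20 = 5.5 | 1.45 | 13.8 | 1.204 |
| 3, 3, 3, 3, 2, 2, 2, 2 | 52/20 = 2.6 | 1.16 | 17.2 | 1.077 |
| 10 clinics of 2 | 40/20 = 2.0 | 1.10 | 18.2 | 1.049 |

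**Step 2: type I error of the exact signed-rank test.** Its attained size at n = 20 is 4.8%. Simulated rates, with at least 100,000 runs per cell:

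| Layout | ICC 0 | 0.02 | 0.05 | 0.10 | 0.20 |
|---|---|---|---|---|---|
| 5 clinics of 4 | 4.9% | 5.5% | 6.4% | 8.2% | 11.6% |
| 8, 5, 4, 2, 1 | 4.9% | 5.8% | 7.4% | 9.9% | 14.9% |
| 3, 3, 3, 3, 2, 2, 2, 2 | – | – | 5.8% | 6.6% | – |
| 10 clinics of 2 | 4.9% | 5.2% | 5.4% | 5.8% | 7.1% |

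Section 8.1 states a directional hypothesis ("The Checkup Coach intervention will increase providers' HPV vaccine recommendation quality score"). A one-sided 5% test at ICC 0.10 gives 7.2% (5 of 4), 8.4% (uneven) and 5.7% (10 of 2). Rounding changes to integers, with ties and zeros, barely alters the two-sided figures.

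**Step 3: incomplete follow-up.** Providers may skip survey questions (section 2.3.1), withdraw fully (section 5.4.3) or attend only the workshop (section 6.1). With 15 analysed as five clinics of 3, type I error is 5.9% at ICC 0.05 and 6.9% at 0.10. With 6, 4, 3, 1, 1 it is 8.2% at ICC 0.10. Losses could also leave clinics more uneven, so in these layouts the effect shrinks but does not vanish.

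**Step 4: what a clinic-level check would deliver.** Take the mean of the clinic mean changes with a 95% t interval on (clinics − 1) degrees of freedom. Width is relative to the provider-level t interval; power is at an assumed change of 0.65 SD.

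| Layout | Width, ICC 0 | Width, ICC 0.10 | Power, ICC 0 | Power, ICC 0.10 |
|---|---|---|---|---|
| 5 clinics of 4 | 1.26 | 1.45 | 60% | 49% |
| 8, 5, 4, 2, 1 | 1.60 | 1.74 | 45% | 39% |
| 10 clinics of 2 | 1.07 | 1.12 | 73% | 70% |

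The signed-rank test has 77% power at ICC 0. For the same three layouts at ICC 0.10 the design effect alone calls for widening by 14%, 20% and 5%, against the 45%, 74% and 12% obtained. The rest comes from the few degrees of freedom and, in the uneven layout, from giving a one-provider clinic the weight of one with eight. Nor does the method deal with correlation by workshop session. With five clinics of 4 crossed with four assumed sessions and a session ICC of 0.10, coverage is 91.0%, against 90.2% for the provider-level interval.

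**The case for a change.** The strongest case for acting is that the facts are not in dispute and the request is cheap. Recruitment is by clinic, the plan ignores clinic, and the test's assumption is unstated. With few or uneven clinics and an ICC of 0.10, the error rate approaches 10%. Section 8.2 says that a hypothesis will be tested, so the p-value is not merely decorative, and it cites the number of clinics as a strength. Without the layout, a reader cannot tell whether the benign ten-clinic case or the uneven one applies. The clinic-mean interval kept its type I error at or below about 5% for clinic correlation, and as a supportive analysis it would leave the primary test untouched.

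The description of the assumption stands, and so does the usefulness of the counts. The case for changing the plan does not. The harm needs correlation in the change, and the documents do not show it: the clinic graphs display vaccination coverage, not the self-reported index. Five equal clinics is the least favourable equal-size layout that section 8.2 allows, and the uneven layout is invented. The link to planning is also indirect, because section 2.2 describes the later study as a "randomized controlled trial to examine the impact of the Checkup Coach intervention on HPV vaccine uptake", which is a different outcome. Finally, a supportive interval that is 26% to 60% wider with no correlation, in the five-clinic layouts, could not tell a reader whether clustering or lost degrees of freedom was the cause.

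**Conclusion.** No change to the plan is needed. Independence of providers is a real, unstated assumption of section 8.4. If it fails, the p-value is moderately too small: about 8% type I error for five clinics of 4, 6.5% for eight clinics and 6% for ten clinics of 2. These figures assume ICC 0.10, a two-sided 5% test, normal changes and complete data from 20 providers. The excess is under one point at ICC 0.02 or below, and reaches 9.9% only in an illustrative uneven layout at ICC 0.10. Larger figures need an ICC of 0.20. The mean change is not biased by this alone, and no stated figure, interval or decision rule in the plan is shown to be wrong.

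Keeping the provider-level test is a fair trade-off in a single-arm feasibility study of this size. The clinic-level alternative costs more precision than the problem would, weights clinics oddly and misses session effects. Labelling the p-value exploratory would not follow from clustering either. What remains is a gap that analysts can sensibly fill when reporting: the number of analysed providers per clinic and, where recorded, per workshop session, with a sentence saying that the tests treat providers as changing independently.

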| 9.6 | Study Discontinuation..... | 15 |
| 9.7 | Future Use of Stored Specimens..... | 16 |

PROTOCOL SUMMARY

Title:

Evaluating the Feasibility of a Mobile Coaching Intervention to Improve HPV Vaccine Delivery

Summary:

The purpose of this study is to examine the feasibility of using Checkup Coach, a mobile coaching intervention, to improve the way that primary care providers recommend HPV vaccination to adolescent patients and their parents. To conduct this feasibility study, we will deliver the Checkup Coach intervention to Kaiser Permanente Washington primary care providers who routinely recommend HPV vaccine to adolescent patients. We will use a single-arm, pre-post design. Participating primary care providers will attend a 1-hour virtual communication workshop and then use a mobile phone app to receive additional coaching for 12 weeks. Providers will complete surveys at three time points: before the communication workshop, immediately after the workshop, and at 12-week follow-up. Surveys will assess changes in providers' self-reported HPV vaccine recommendation practices and beliefs about HPV vaccine, as well as the acceptability of the intervention. We hypothesize that providers' HPV vaccine communication will improve between baseline and 12-week follow-up.

Objectives:

To evaluate whether the Checkup Coach intervention improves providers' HPV vaccine recommendation quality.

Primary outcome measure: The change in providers' composite score on a 5-item index of self-reported use of HPV vaccine communication practices from baseline to 12-weeks post-intervention.

Sample:

[figure not shown]
Primary care providers who treat 11-12 year old patients in participating Kaiser Permanente Washington pediatric and family medicine practices.

Phase:

Not applicable

| | |
|---|---|
| Study Duration: | June 21, 2021 through January 14, 2022 |
| Participation Duration: | Providers will attend a one-hour communication training workshop and use the Checkup Coach mobile phone app at their discretion for 12 weeks. |
| Description of Intervention: | The Checkup Coach intervention is a 1-hour virtual workshop on HPV vaccine communication, followed by 12 weeks of access to a mobile app that provides additional coaching. |
| Estimated Time to Complete Enrollment: | 4 months |

Schematic of Study Design:

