4 STUDY DESIGN

This study will evaluate the Checkup Coach intervention using a single-arm, pre-post design with approximately 20 primary care providers at Kaiser Permanente Washington (KPWA). The intervention has two main components. In the first part of the intervention, participants attend a communication training workshop via a virtual conferencing platform. The workshop will be conducted by study staff and the KPWA Director of Preventive Care. The brief (<1 hour) workshop reviews evidence on HPV vaccination, models guideline-consistent recommendation practices, trains providers to address common parent concerns, and facilitates discussion of shared goals for improving. Workshop content is evidence-based and reflects communication practices supported by research evidence and recommended by the Centers for Disease Control and Prevention. At the end of the workshop, providers are asked to download and practice using the Checkup Coach mobile app.

In the second part of the intervention, which starts after the communication training, providers are invited to use the Checkup Coach mobile app for 12 weeks. The app is a QI tool designed to provide tips and tools for improving HPV vaccine communication. App functions include: (a) provider self-assessment of HPV vaccine recommendation practices; (b) feedback on their HPV recommendation quality in the form of a “recommendation goal score”; (c) research-tested messages for addressing parent concerns that are tailored to in-app self-assessments; and (d) a dashboard with graphs of provider- and clinic-level HPV vaccination coverage (i.e. % of 11-12 year old adolescents vaccinated).

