6 STUDY INTERVENTION

6.1 Study Intervention Description

The Checkup Coach intervention offers two main components to primary care providers who care for adolescent patients: a webinar communication workshop and use of the Checkup Coach mobile app.

1. Communication Workshop. The Checkup Coach intervention begins with a brief (<1 hour), communication training workshop. Using a script and slides, the KPWA Director for Preventive Care and the study PI will meet with participating providers over a web-based meeting platform to: review evidence on HPV vaccination; model high-quality, guideline-consistent recommendations; train providers to address parent concerns; and facilitate discussion of shared goals for improving.

At the end of the training, providers will be asked to download and begin using the Checkup Coach app. Downloading and using the app will be voluntary, and providers can consent to participate in the webinar training but decline all other study activities.

2. Checkup Coach app. Providers will be invited to use the Checkup coach mobile app at their discretion for the 12 week study period. If they have push notifications enabled, providers will be sent push notifications reminding them to use the app up to six times over the 12 week period. Providers will complete the in-app self-assessments and receive tailored feedback every time they use the app.

A detailed description of the Checkup Coach self-assessment and tailored feedback is as follows:

- Self-assessment of recommendation quality. Providers complete a very brief in-app self-assessment to determine how often in the last week they used 5 practices effective for recommending HPV vaccine according to national guidelines. Guidelines include delivering recommendations on time (i.e., ages 11-12), consistently to all eligible patients, and offering same-day vaccination services when possible. The app adds 5-point

response options to give an overall score and to identify areas for improvement.

- Recommendation Goal Score. The app displays a bar chart of providers' overall self-assessed recommendation quality score in reference to the goal of 5 (i.e., "almost always" using all 5 practices).
- Dashboard. The app presents line graphs of aggregate HPV vaccination coverage (i.e., % of patients vaccinated) over the study period for both the individual provider and their clinic.

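### Does section 8.4 need a post-workshop to 12-week comparison of the belief, social-environment and knowledge items?

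*Combined protocol and SAP*

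**What the plan says.** The Protocol Summary sets three survey times: "before the communication workshop, immediately after the workshop, and at 12-week follow-up". Section 4 places the 12 weeks of app use after the workshop, so the second and third surveys enclose the app phase.

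Section 8.4 treats two groups of measures differently:

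- **Primary index:** "we will compare providers' mean recommendation quality index scores between baseline and 12-week follow-up using Wilcoxon signed-rank tests".
- **Cognition and social-environment items and the knowledge index:** Wilcoxon signed-rank tests "between the baseline and post-workshop surveys and the baseline and 12-week follow-up surveys". That is two of the three possible pairs. Post-workshop against 12 weeks is not planned.

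Section 8.2 gives the sample size as "over the 12-week study period with approximately 20 providers", with no SD, effect size or power behind it. It states the aim as follows: "The purpose of a feasibility study is to estimate effect sizes for powering a large-scale RCT".

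**The concern.** The workshop is a single event and the app is meant to carry its effect forward, so it is natural to ask whether gains were kept, grew or faded between the second and third surveys. The items are measured at both times, yet the plan compares each time only with baseline.

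The two planned results do not stand in for the missing one:

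- Both tests can be significant whether the gain is fading or growing.
- Subtracting the two mean changes gives the paired change only if the same providers answered all three surveys. Section 6.1 says that "providers can consent to participate in the webinar training but decline all other study activities", and 8.4 does not say who enters each comparison.
- Even with identical providers, the interval for the difference needs the correlation between the two changes.

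If persistence on these items were a question of the trial, 8.4 would leave it unanswered although the data are in hand, and the planning of the later RCT would be the poorer for it.

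**Working it through.** **Step 1. Does the plan ask the question?** The relevant sections, side by side:

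| Section | What it commits to |
|---|---|
| 8.1 | One hypothesis: the intervention raises the recommendation quality score |
| 3.2.1 | Primary outcome: change in that score, baseline to 12 weeks |
| 3.2.2 | Other measures: app use and acceptability |
| Protocol Summary | Surveys assess changes in practices and beliefs, plus acceptability |
| 8.4 | Belief, social-environment and knowledge items: change from baseline at each later survey |

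The belief, social-environment and knowledge items are not listed among the outcome measures in 3.2 to 3.2.2. What the Protocol Summary and 8.4 promise for them is an assessment of change, and the two comparisons with baseline deliver it. No section sets persistence from the second to the third survey as an objective.

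**Step 2. Does the aim in 8.2 bring it in?** The effect sizes there are for powering an RCT, and section 2.2 says that RCT would examine vaccine uptake. The hypothesis named in 8.2 itself concerns overall recommendation quality. A within-arm change on single belief items between two follow-up surveys is not an effect size from which such a trial would be powered.

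**Step 3. Can the planned tests hide the trajectory?** Yes. The documents give no SD, correlation or effect for these items, so all inputs here are assumptions. With 20 providers, SD 1.0 for each change from baseline and correlation 0.5, 4,000 simulated trials per scenario gave:

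| True change from baseline (post-workshop, 12 weeks) | Both planned tests significant | Test of the extra contrast significant |
|---|---|---|
| +1.3, then +0.8 (fading) | 0.913 | 0.544 |
| +0.8, then +1.3 (growing) | 0.910 | 0.534 |

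So the two p-values do not separate opposite paths. That would count against the plan only if it drew a conclusion about the path from them, and it does not.

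**Step 4. Can subtraction mislead?** Also yes. Suppose 20 providers answer after the workshop and 15 of them answer again at 12 weeks. The 15 gained 0.8, the other 5 gained 0, and the 15 stand at +0.6 at 12 weeks.

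- Mean change after the workshop: (15 × 0.8 + 5 × 0)/20 = 0.60.
- Mean change at 12 weeks: 0.60.
- Difference by subtraction: 0.60 − 0.60 = 0.0.
- Paired change in the 15: 0.6 − 0.8 = −0.2.

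The arithmetic is right, but 8.4 does not plan the subtraction, and each of the two means is correct for the providers in it.

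**Step 5. What would the extra estimate tell us?** If both changes from baseline have SD 1.0 and correlation r, the post-workshop to 12-week change has SD √(2(1 − r)). The 95% half-width is t(0.975, n − 1) × SD/√n, with t = 2.093 for n = 20 and 2.145 for n = 15.

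| r | SD | Half-width, n = 20 | Half-width, n = 15 | Interval around −0.2, n = 15 | Chance it excludes zero, n = 15 |
|---|---|---|---|---|---|
| 0.2 | 1.265 | 0.59 | 0.70 | −0.90 to 0.50 | 9% |
| 0.5 | 1.000 | 0.47 | 0.55 | −0.75 to 0.35 | 11% |
| 0.8 | 0.632 | 0.30 | 0.35 | −0.55 to 0.15 | 21% |

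The last column is the noncentral t probability for a true change of −0.2. At all three correlations the interval centred on −0.2 covers both fading and growth.

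**The case for a change.** The strongest opposing case is that the data will exist, that one descriptive line per item costs almost nothing, and that naming it beforehand fixes who is counted and how the result is read. It is also true that reading persistence off the two planned tests would be unsafe. In a second simulation, with items rounded to whole points from 1 to 5, 20 providers, an assumed SD of 0.8, correlation 0.5 and baseline mean 3.2, a constant gain of +0.5 at both surveys left exactly one of the two tests significant in 31.5% of runs. A true fade from +1.0 to +0.6 left both significant in 79%.

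This stands as a caution about interpretation: no claim that gains held or faded should be built on comparing the two p-values. It does not show a fault in what is planned. The direct paired test found that same fade in only 43% of runs, and a change between the last two surveys in a single arm mixes the app, the wearing-off or delayed effect of the workshop, and time trend.

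The point about differing respondents carries less than it seems. A provider who takes only the webinar may answer no survey and then enters no comparison, while section 5.4.3 offers those who leave the intervention continued follow-up. Which providers are analysed is a question for the planned comparisons too, and a separate one.

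**Conclusion.** The concern does not hold. Section 8.4 does omit the post-workshop to 12-week contrast for these secondary items, but no objective, hypothesis or outcome measure calls for it. If the plan is followed to the letter, the primary analysis and both planned comparisons with baseline remain sound.

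This conclusion rests on the text of 2.2, 3.2 to 3.2.2, 8.1, 8.2 and 8.4, and not on any assumed figure. The calculations, which do rest on assumed SDs, correlations and gains, show only that the extra estimate would be imprecise: a half-width of 0.30 to 0.59 points with 20 pairs and 0.35 to 0.70 with 15. The study team may report it later as exploratory, but its absence is not an error in the plan.
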